4.4.5 Management and Dose Modifications for Pneumonitis

Pneumonitis has been observed in subjects receiving trametinib in combination with dabrafenib. To reduce the risk of pneumonitis, subjects will be monitored closely for symptoms, and evaluated with imaging and functional tests. Dose modification and supportive care guidelines for pneumonitis are described in the table below.

CTCAE Grade	Management of Pneumonitis	Action and Dose Modification for Dabrafenib and Trametinib
1	CT scan (high-resolution with lung windows) recommended Clinical evaluation and laboratory work-up for infection Monitoring of oxygenation via pulse-oximetry recommended Consultation of pulmonologist recommended	Continue study treatment at current dose
2	CT scan (high-resolution with lung windows) Clinical evaluation and laboratory work-up for infection Consult pulmonologist Pulmonary function tests -if < normal, repeat every 8 weeks until ≥ normal Bronchoscopy with biopsy and/or bronchioalveolar lavage (BAL) recommended Symptomatic therapy including corticosteroids if clinically indicated	Interrupt study treatment until recovery to grade ≤1 Restart with study treatment reduced by one dose level Escalation to previous dose level after 4 weeks possible after consultation with study PI If no recovery to grade ≤1 within 4 weeks, permanently discontinue study treatment
3	CT scan (high-resolution with lung windows) Clinical evaluation and laboratory work-up for infection Consult pulmonologist Pulmonary function tests-if < normal, repeat every 8 weeks until ≥ normal Bronchoscopy with biopsy and/or BAL if possible Symptomatic therapy including corticosteroids as clinically indicated	Interrupt study treatment until recovery to grade ≤1 After consultation with study PI, study treatment may be restarted reduced by one dose level If no recovery to grade ≤1 within 4 weeks, permanently discontinue study treatment
4	Same as grade 3	Permanently discontinue study treatment

4.4.6 Management and Dose Modifications for Renal Insufficiency

Cases of renal insufficiency have occurred in subjects receiving dabrafenib and the combination of dabrafenib and trametinib.

Prior to start of study treatment, concomitant medications should be reviewed for the potential risk of inducing nephrotoxicity and concomitant medications should be modified if clinically possible. Guidelines regarding management and dose

reduction for renal insufficiency considered to be related to study treatment by the investigator are provided in the table below.

Serum Creatinine (SCr) Level	Management of Renal Insufficiency	Action and Dose Modification for Dabrafenib and Trametinib

SCr increase >0.2 mg/dL (18 µmol/L)
 
But
 
≤0.5 mg/dL (44 µmol/L) above baseline
	
Recheck SCr within 1 week
 
SCr increase lasts > 1 week: contact Study PI; If elevation persists beyond 4 weeks, recommend evaluation (consider renal biopsy) for etiology; consider nephrology consultation.
 
If pyrexia is present, treat pyrexia per guidelines^a; please note NSAIDS can induce renal insufficiency, especially in subjects with dehydration; encourage oral fluids
	
Continue study treatment at the same dose level

SCr increase >0.5 mg/dL (44 µmol/L) above baseline
 
Or
 
SCr >2 mg/dL (> 177 µmol/L)
	
Monitor SCr ≥ 2 times per week
 
Hospitalization may be necessary if serum creatinine cannot be monitored at least twice weekly
 
If pyrexia is present, treat pyrexia per guidelines^a
 
Consult nephrologist if clinically indicated
 
Perform renal biopsy if clinically indicated, for example:
 
 Renal insufficiency persists despite volume repletion Subject has new rash or signs of hypersensitivity (such as elevated eosinophil count) 	
Interrupt study treatment until SCr recovers to baseline
 
Restart with study treatment^b


^aNSAIDs can induce renal insufficiency, especially in subjects with dehydration; encourage oral fluids or consider intravenous fluids as clinically indicated. See guidelines for pyrexia in section 4.4.7
 
^bInvestigator may restart at either the same or a reduced dose level. Escalation of study treatment to previous dose level is allowed if another episode of renal insufficiency does not occur after 4 weeks of dose reduction. Consultation with study PI is required before restarting study treatment if there is evidence of thrombotic microangiopathy.
		

4.4.7 Management and Dose Modifications for Diarrhea

Episodes of diarrhea have occurred in subjects receiving dabrafenib, trametinib, or both therapies in combination. Other, frequent causes for diarrhea including concomitant medications (e.g., stool softeners, laxatives, antacids), infections by *C. difficile* or other pathogens, partial bowel obstruction, etc., should be clinically excluded. **Note:** loperamide should be made available prior to start of study treatment to patient so loperamide administration can begin at the first signs of diarrhea. Guidelines regarding management and dose reduction for diarrhea considered to be related to study treatment by the investigator are provided in the table below.

CTCAE Grade	Diarrhea Management	Action and Dose Modification for Dabrafenib and Trametinib
Uncomplicated Diarrhea ^a Grade 1 or 2	
Diet: stop all lactose containing products; eat small meals, BRAT-diet (banana, rice, apples, toast) recommended
 
Hydration: 8-10 large glasses of clear liquids per day (e.g., Gatorade or broth)
 
Loperamide: initially 4 mg, followed by 2 mg every four hours or after every unformed stool; maximum 16 mg/day. Continue until diarrhea free for 12 hours
 
Diarrhea > 24h: loperamide 2 mg every two hours; maximum 16 mg/day. Consider adding oral antibiotics
 
Diarrhea > 48h: loperamide 2 mg every two hours; maximum 16 mg/day. Add budesonide or other second-line therapies (octreotide, or tincture of opium) and oral antibiotics
	
Continue study treatment
 
If diarrhea is grade 2 for > 48h, interrupt study treatment until diarrhea resolves to grade ≤1
 
Restart study treatment at the same dose level

Uncomplicated Diarrhea ^a Grade 3 or 4 OR Any Complicated Diarrhea ^b	
Clinical evaluation mandatory
 
Loperamide: initially 4 mg, followed by 2 mg every four hours or after every unformed stool; maximum 16 mg/day. Continue until diarrhea free for 12 hours
 
Oral antibiotics and second-line therapies if clinically indicated
 
Hydration: intravenous fluids if clinically indicated
 
Antibiotics (oral or intravenous) if clinically indicated
 
Intervention should be continued until the subject is diarrhea free for ≥ 24 hours
 
Intervention may require hospitalization for subjects at risk of life-threatening complications
	
Interrupt study treatment until diarrhea resolves to grade ≤1
 
Restart with study treatment reduced by one dose level^c
 
If 3 dose reductions of study treatment are clinically indicated, permanently discontinue study treatment

^a Uncomplicated diarrhea defined by the absence of symptoms such as cramping, nausea/vomiting ≥grade 2, decreased performance status, pyrexia, sepsis, neutropenia grade ≥3, frank bleeding, and/or dehydration requiring intravenous fluid substitution
 
^b Complicated diarrhea is diarrhea in the presence of symptoms noted under footnote (a)
 
^c Escalation of study treatment to previous dose level is allowed after consultation with the PI and in the absence of another episode of complicated or severe diarrhea in the 4 weeks subsequent to dose reduction.
		

4.4.8 Management and Dose Modification Guidelines for Therapy-related Pyrexia

Pyrexia is defined as $\geq 38.5^{\circ}\text{C}$ or 101.3°F . Episodes of pyrexia have been observed in subjects receiving dabrafenib monotherapy and is increased in incidence and severity in subjects receiving dabrafenib in combination with trametinib. (Pyrexia is also a side effect of trametinib, but is less frequent than that associated with dabrafenib-see section 5.1.5). [6] In a minority of cases the pyrexia was accompanied by symptoms such as severe chills, dehydration, hypotension, dizziness or weakness. Pyrexia accompanied by hypotension, dehydration requiring IV fluids, or severe rigors/chills should be reported as an SAE (see section 7.3.3). Subjects should be instructed on the importance of immediately reporting febrile episodes. In the event of a fever, the subject should be instructed to take non-steroidal anti-pyretics (e.g., ibuprofen), acetaminophen or other suitable anti-pyretic medication as appropriate to control fever. The use of oral corticosteroids should be considered in those instances in which anti-pyretics are insufficient. In subjects experiencing pyrexia associated with rigors, severe chills, dehydration, hypotension, etc., renal function should be monitored carefully.

For each episode of pyrexia (defined above), a thorough clinical examination (including blood pressure) for signs and symptoms of infection or hypersensitivity is required; laboratory work-up should include full blood count, electrolytes, creatinine, BUN, CRP, liver function tests, blood culture, and urine culture. For subjects experiencing pyrexia complicated by rigors, severe chills, etc., a clinical evaluation and laboratory work-up is mandatory for each event; anti-pyretic treatment should be started immediately at the first occurrence and prophylactic anti-pyretic treatment is recommended. This prophylactic treatment may be discontinued after 3 days in the absence of pyrexia.

Oral hydration should be encouraged in subjects without evidence of dehydration. Intravenous hydration is recommended in subjects experiencing pyrexia complicated by dehydration/hypotension.

Pyrexia Management	Action and Dose Modification

1st Event Clinical evaluation for infection and hypersensitivity
 
Laboratory work-up^a
 
Hydration as required
 
Administer anti-pyretic treatment if clinically indicated and initiate prophylactic treatment^e if fever associated with rigors, renal failure, dehydration or hypotension
 
2nd Event^b Clinical evaluation for infection and hypersensitivity
 
Laboratory work-up^a
 
Hydration as required
 
Within 3 days of onset of pyrexia:
 
 Optimize anti-pyretic therapy Consider oral corticosteroids (i.e., prednisone 10 mg) for at least 5 days or as clinically indicated 
Subsequent Events: Clinical evaluation for infection and hypersensitivity
 
Laboratory work-up^a
 
Hydration as required^d
 
Within 3 days of onset of pyrexia:
 
 Optimize oral corticosteroid dose as clinically indicated for recalcitrant pyrexia^b If corticosteroids have been tapered and pyrexia recurs, restart steroids If corticosteroids cannot be tapered consult study PI 	
1st Event: Interrupt dabrafenib
 
Continue trametinib (unless fever >104°F or fever complicated by rigors, hypotension, dehydration or renal failure, in which case trametinib should be withheld until fever resolves.) Resume at same or lower dose level.
 
Once pyrexia resolves to baseline, restart dabrafenib at the same dose level
 
If fever was associated with rigors, renal failure, dehydration or hypotension, reduce dabrafenib by one dose level^c
 
2nd Event: Interrupt dabrafenib
 
Continue trametinib (unless fever >104°F or fever complicated by rigors, hypotension, dehydration or renal failure, in which case trametinib should be withheld until fever resolves.) Resume at same or lower dose level.
 
Once pyrexia resolves to baseline, restart dabrafenib at the same dose level
 
If fever was associated with rigors, renal failure, dehydration or hypotension, reduce dabrafenib by one dose level
 
Subsequent Events: Interrupt dabrafenib
 
Continue trametinib (unless fever >104°F or fever complicated by rigors, hypotension, dehydration or renal failure, in which case trametinib should be withheld until fever resolves.) Resume at same or lower dose level.
 
Once pyrexia resolves to baseline, restart dabrafenib reduced by one dose level^c
 
If dabrafenib must be reduced to <75 mg BID, permanently discontinue both study treatments


^aTo include CBC with diff, electrolytes, creatinine, BUN, CRP, liver function tests, blood culture, and urine culture.
^bIn subject experiencing pyrexia complicated by rigors, severe chills, etc., which cannot be controlled with anti-pyretic medication, oral corticosteroids should be started at the 2nd event and doses should be gradually increased for subsequent events.
^cDabrafenib should be reduced by one dose level after three episodes of pyrexia complicated by rigors, severe chills, etc., which cannot be managed by best supportive care and increasing doses of oral steroids. Escalation of dabrafenib is allowed if no episode of pyrexia is observed in the 4 weeks subsequent to dose reduction.
^dOral hydration should be encouraged in subjects without evidence of dehydration. Intravenous hydration is recommended in subjects experiencing pyrexia complicated by dehydration/hypotension.
^eProphylactic anti-pyretic treatment may be discontinued after 3 days in the absence of pyrexia

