1.5.1 Summary Safety Information of the Combination

Most subjects treated with combination therapy experienced an adverse event. In both studies, pyrexia was the most frequently reported AE, and the most frequently reported grade 3 event (presented with *) in subjects treated with combination therapy (51%/6%*) in Study MEK115306 and 57%/4%* in Study BRF113220). AEs that occurred in >30% of subjects treated with combination therapy in either study included pyrexia, fatigue, vomiting, chills, nausea, and headache.

Grade 4 AEs reported in more than a single subject treated with combination therapy included neutropenia (3 subjects in Study BRF113220) pyrexia (2 subjects in Study BRF113220). AEs leading to permanent discontinuation were reported in <10% of subjects treated with combination therapy in either study.

The most common SAEs in both studies were pyrexia and chills. Fatal SAEs have been reported in 4 subjects in the combination therapy arm in Study MEK115306 and 3 subjects in the 3 subjects in the 150mg/2mg combination therapy arm in the Study BRF113220 pooled combination therapy population. One fatal SAE was reported in 2 subjects in Study MEK115306 (cerebral hemorrhage).

In general, the overall profile of AEs of special interest observed in subjects treated with combination therapy is consistent with the known profiles of each separate drug. The most notable differences were the increase in Grade 3 pyrexia and hepatic events and the decrease in skin-related toxicities with combination therapy relative to monotherapy.

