4.4 Dose Modifications for Trametinib and Dabrafenib for Toxicity

See sections 5.1.5, 5.2.5, and appendices (section 11.3), and the respective IBs for additional information on drug-related toxicities. Any patient who receives treatment on this protocol will be evaluable for toxicity. Each patient will be assessed every 3 weeks for the development of any toxicity according to the Time and Events table (see Section 6.0). Toxicity will be assessed according to the NCI CTCAE, v 4.

If a patient experiences ≥ 2 or more AEs simultaneously that require different dose reductions, the lower dose should be used. Unless otherwise noted in the following sections, a maximum of 2 dose-level reductions for AEs are allowed on this protocol. If >2 dose reductions are required, protocol therapy is to be discontinued and patient is to be followed per protocol.

With the exception of decreased LVEF, both therapies should be reduced simultaneously in response to toxicities that are considered by the investigator to be treatment related. Note that if dabrafenib is permanently discontinued, trametinib will also be permanently discontinued.

Unless otherwise noted in the tables below, if an AE resolves to grade 1 or baseline at the reduced dose level, and no additional toxicities are seen after 4 weeks of study treatment at the reduced dose, the dose may be increased to the previous dose level in consultation with the study PI if so noted in the tables.

For AEs that require dose reductions, please refer to the dose levels in the following tables.

Trametinib Dose Levels for Toxicity		
Dose Levels	Dose, Route and Schedule	Dosage Strength
0	2 mg PO QD	2.0 mg tablets
-1	1.5 mg PO QD	0.5mg tablets
-2	1 mg PO QD	0.5mg tablets

Dabrafenib Dose Levels for Toxicity		
Dose Levels	Dose, Route and Schedule	Dosage Strength
0	150 mg PO BID	75 mg capsules
-1	100 mg PO BID	50 mg capsules
-2	75 mg PO BID	75 mg capsules

A dose reduction below 75 mg BID for dabrafenib and 1 mg once daily for trametinib is not allowed. If a dose reduction below 75 mg BID for dabrafenib is required, trametinib will also be permanently discontinued. If a dose reduction below 1.0 mg once daily for trametinib is required, then trametinib will be permanently discontinued, but these subjects will be allowed to continue dabrafenib.

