Symptoms usually resolve within 2-4 weeks of treatment cessation.

CTCAE Grade	Management of HFSR	Action and Dose Modification for HFSR for Dabrafenib and Trametinib
1	Lifestyle changes recommended Initiate symptomatic treatment if clinically appropriate	Continue study treatment at current dose level
2	Lifestyle changes recommended Initiate symptomatic treatment	Interrupt study treatment until recovery to \leq grade 1 Recovery to \leqgrade 1 within 7 days: Restart study treatment at previous dose level No recovery to grade \leq1 within 7 days or \geq 2nd occurrence: restart with study treatment reduced by one dose level^a
3	Lifestyle changes recommended Initiate symptomatic treatment Consider consulting dermatologist	Interrupt study treatment until recovery to \leq grade 1 Restart with study treatment reduced by one dose level^a If 3 rd occurrence, discontinue study treatment permanently
^a Escalation of study treatment to the previous dose level is allowed if no HFSR is observed in the 4 weeks subsequent to dose reduction.		

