(Scenario A) Asymptomatic and persistent (terms defined above) SBP of >140 and <160 mmHg, or DBP >90 and <100 mmHg, or Clinically significant increase in DBP of 20 mmHg (but still below 100 mmHg).	Continue study treatment at the current dose Adjust current or initiate new antihypertensive medication Titrate antihypertensive medication(s) during the next 2 weeks as indicated to achieve well-controlled ^a BP If BP is not well controlled within 2 weeks, consider referral to a specialist and go to scenario (B).
(Scenario B) Asymptomatic SBP >160 mmHg, or DBP >100 mmHg, or Failure to achieve well-controlled BP within 2 weeks in Scenario A	Interrupt study treatment if clinically indicated Adjust current or initiate new antihypertensive medication(s) Titrate antihypertensive medication(s) during the next 2 weeks as indicated to achieve well-controlled BP ^a Once BP is well controlled ^a , restart study treatment reduced by one dose level^c
(Scenario C) Symptomatic ^b hypertension or Asymptomatic and persistent (term defined above) SBP ≥160 mmHg, or DBP ≥100 mmHg, despite antihypertensive medication and dose reduction of study treatment	Interrupt study treatment Adjust current or initiate new antihypertensive medication(s) Titrate antihypertensive medication during the next 2 weeks as indicated to achieve well-controlled BP ^a Referral to a specialist for further evaluation and follow-up is recommended Once BP is well controlled ^a , restart study treatment reduced by one dose level
Scenario D) Refractory hypertension unresponsive to above interventions or hypertensive crisis.	Permanently discontinue study treatment Continue follow-up per protocol.
^a Well-controlled blood pressure defined as SBP ≤140 mm Hg and DBP ≤90 mm Hg in two separate readings during up to three consecutive visits. ^b Symptomatic hypertension defined as hypertension aggravated by symptoms (e.g., headache, light-headedness, vertigo, tinnitus, episodes of fainting) that resolve after the blood pressure is controlled within the normal range. ^c Escalation of trametinib to previous dose level can be considered if BPs remain well-controlled for 4 weeks after restarting of trametinib. Approval from study PI is required.	

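### In the section 4.4.8 pyrexia table, the 1st-event row cuts dabrafenib after one complicated fever, its own footnote c after three, and no text says which governs

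*Combined protocol and SAP*

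**What the plan says.** The pyrexia table in section 4.4.8 has three tiers. Each interrupts dabrafenib during the fever; they differ in the dose at restart.

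- 1st event: restart at the same dose, with an exception for complicated fever: "If fever was associated with rigors, renal failure, dehydration or hypotension, reduce dabrafenib by one dose level". This line carries marker c.
- 2nd event: the same two instructions in the same words, but without marker c.
- Subsequent events: "Once pyrexia resolves to baseline, restart dabrafenib reduced by one dose level". This line carries marker c and applies to any further fever, complicated or not.

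Footnote c has two sentences. The first puts the one-level cut after three complicated episodes that have resisted supportive care and rising oral steroid doses. The second is a re-escalation rule: "Escalation of dabrafenib is allowed if no episode of pyrexia is observed in the 4 weeks subsequent to dose reduction". Footnote b has steroids begin at the 2nd event when antipyretics do not control a complicated fever, with higher doses later.

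Section 4.4 sets the dabrafenib levels at 150, 100 and 75 mg BID. It states that, unless otherwise noted, "a maximum of 2 dose-level reductions for AEs are allowed on this protocol". It lets the dose go back up after consultation with the study PI where the tables note this.

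**The concern.** A footnote should explain or qualify the line it is attached to. Here its first sentence sets a condition that the marked line can never meet. A physician looking up the restart dose after a complicated first fever finds one trigger in the cell and a much later one in the note.

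The event is not a rare one for this regimen. Section 1.5.1 says that "pyrexia was the most frequently reported AE, and the most frequently reported grade 3 event", with any-grade and grade 3 rates of 51% and 6% in one study and 57% and 4% in the other. Section 7.1.4 makes fever with rigors or with hypotension reportable as serious even without a hospital stay. Section 1.5.2 says that about half of the patients with pyrexia had a single event. For them a three-episode trigger could never apply, so the 1st-event instruction is the only one that matters.

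What is at stake is the restart dose and whether physicians apply it consistently. The cut also uses one of the two reductions that section 4.4 allows.

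**Working it through.** There is no planned figure to reproduce. The check compares the instructions, looks for a rule that settles them, and works out the dose difference.

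**1. Triggers for a one-level dabrafenib cut.**

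| Place in 4.4.8 | Episodes needed | Must be complicated? | Must have resisted steroids? | Marker c? |
|---|---|---|---|---|
| 1st-event row | 1 | yes | no | yes |
| 2nd-event row | 2nd event | yes | no | no |
| Subsequent-events row | any after the 2nd | no | no | yes |
| Footnote c, first sentence | 3 | yes | yes | – |

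**2. Can a first event satisfy footnote c?** No. The count alone rules it out, since a first episode is not a third. Footnote b points the same way, because rising steroid doses are planned only from the 2nd event.

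**3. Could footnote c be an additional trigger?** The rows already cut the dose at a complicated 1st or 2nd fever and at every later fever. A threshold of three complicated, uncontrolled episodes would then never add a cut. So the sentence either conflicts with the row or does nothing.

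**4. How do the comparable tables use this kind of footnote?** In each, the note on a one-level cut deals only with going back up:

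- Hand-foot skin reaction (4.4.2.4): "Escalation of study treatment to the previous dose level is allowed if no HFSR is observed in the 4 weeks subsequent to dose reduction".
- Hypertension (4.4.3.1): "Escalation of trametinib to previous dose level can be considered if BPs remain well-controlled for 4 weeks after restarting of trametinib".
- Diarrhea (4.4.7): "Escalation of study treatment to previous dose level is allowed after consultation with the PI and in the absence of another episode of complicated", the condition continuing to cover severe diarrhea over 4 weeks.

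The second sentence of footnote c fits this pattern and the first does not. This suggests that the row is the intended rule, but it is an inference.

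**5. Does any other text decide?** The lower-dose rule in 4.4 covers two or more adverse events at the same time, not a row against its own footnote. The cap of two reductions does not say which trigger applies. Section 5.2.7 covers holding the drug, and 7.1.4 covers reporting. None gives precedence.

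**6. Size, for one complicated first fever in a patient on 150 mg BID.**

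- Row: 2 × 100 = 200 mg/day, with 1 of the 2 allowed reductions used.
- Footnote c read as a qualifier: 2 × 150 = 300 mg/day, with no reduction used.
- Relative difference: 1 − 200/300 = 33%.

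**7. Not computed.** The documents give no rate of complicated first fever. Grade 3 is not the table's trigger, so the 6% and 4% cannot stand in for it.

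**The case against.** The strongest reply is that the two instructions do not exclude each other. The row is an explicit order for a defined event. Footnote c does not say that the cut comes only after three episodes, and it forbids no earlier cut. A physician who follows the rows never breaches it. The 150 mg BID restart arises only if someone reads the footnote as overriding the cell. This largely stands, and it is why the practical divergence is modest. It does not remove the problem: the note is attached to that very line, and reading it as a qualifier is an ordinary thing to do with a footnote.

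Second, the conflict at the first event depends on one superscript, which the otherwise identical 2nd-event line lacks. If marker c belonged only on the subsequent-events line, the sharpest part of the point would largely fall away. The episode count would then fit, although the footnote would still ask for complication and steroid failure where the row asks for neither. The available text shows the marker on the 1st-event line, and nothing in it points to a misplacement.

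Third, the oversight is real: dabrafenib is stopped during the fever, serious events are recorded within 24 hours (7.3.2), and the PI monitors safety continuously (7.4). These cases would be seen. None of these provisions sets the restart dose.

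**Conclusion.** The inconsistency is real and confined to one footnote sentence. The row is the better reading, but the protocol does not say so. For one complicated first fever from full dose, the restart could be 100 or 150 mg BID, a 33% difference between two permitted levels. That is a difference in dose, not a measured difference in risk. It is worth correcting because it concerns an operative dosing rule for the regimen's most frequent adverse event and costs almost nothing to settle.

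A reader might infer more than the documents support:

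- **That treatment paths diverge sharply.** Under the rows, three complicated fevers would take dabrafenib from 150 to 100 to 75 mg BID and then stop both drugs. Under footnote c alone, the first cut, to 100 mg BID, would come only at the third. That contrast assumes no re-escalation between fevers and an exclusive reading of the footnote, which its wording does not state.
- **That a number of patients would be misdosed.** Without a rate of complicated first fever, no count can be given.
- **That the primary analysis or power suffers.** Nothing in section 8.1 depends on this rule, and no such effect is claimed.

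**What to change.** Keep the table rows as the operating rule and delete the first sentence of footnote c. The footnote then holds only its re-escalation sentence, subject to the consultation with the study PI that section 4.4 already requires.

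Do not add marker c to the 2nd-event line as a tidy-up. Section 4.4 permits re-escalation only where the tables note it, and that line has no such note. The marker would therefore create a new dosing permission. If the sponsor wants re-escalation after a 2nd-event cut, it should be a separate change, declared as such in the amendment.

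The cost is one deleted sentence in an amendment and a short memo to sites. There are no added procedures or patients, and the sample size does not change.
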